**Table 10. Serious Adverse Event Reporting via Paper CRF**

| Serious Adverse Event Reporting via Paper CRF  |
|---|
| 

• Facsimile transmission of the Serious Adverse Event Report Form (see Appendix B) is the preferred method to transmit this information.

• In rare circumstances and in the absence of facsimile equipment, notification by telephone is acceptable with a copy of the Serious Adverse Event Report Form sent by overnight mail or courier service.

• Initial notification via telephone does not replace the need for the investigator to complete and sign the Serious Adverse Event Report Form within the designated reporting time frames.

• Once the study has ended, serious adverse event(s) should be reported to Amgen (regardless of causality) if the investigator becomes aware of a serious adverse event. The investigator should use the paper-based Serious Adverse Event Contingency Report Form to report the event.

 |

#### **12.2.1.3      Serious Adverse Events after the Protocol-required Reporting Period**

There is no requirement to monitor study subjects for serious adverse events following the protocol-required reporting period or after end of study. However, these serious adverse events should be reported to Amgen (regardless of causality) if the investigator becomes aware of them. Per local requirements in some countries (eg, European Union [EU] member states), investigators are required to report serious adverse events that they become aware of after end of study. If serious adverse events are reported, the investigator is to report them to Amgen within 24 hours following the investigator's knowledge of the event.

Serious adverse events reported outside of the protocol-required reporting period will be captured within the safety database as clinical trial cases for the purposes of expedited reporting.

**If further safety related data is needed to fulfill any regulatory reporting requirements for a reportable event, then additional information may need to be collected from the subject's records after the subject ends the study.**

#### **12.2.1.4 Method of Detecting Adverse Events and Serious Adverse Events**

Care will be taken not to introduce bias when detecting adverse events and/or serious adverse events. Open-ended and non-leading verbal questioning of the subject is the preferred method to inquire about adverse event occurrence.

#### **12.3 Pregnancy and Lactation Reporting**

If a female subject becomes pregnant, or a male subject fathers a child following exposure to the Amgen investigational product (AMG 890 or placebo) report the pregnancy to Amgen Global Patient Safety as specified below.

Investigators should report pregnancies that occur during the study or through 90 days after receiving the Amgen investigational product (AMG 890 or placebo), for subjects who withdraw prior to end of study.

The pregnancy should be reported to Amgen Global Patient Safety within 24 hours of the investigator's knowledge of the pregnancy. Report a pregnancy on the Pregnancy Notification Worksheet ([Appendix C](#)). Amgen Global Patient Safety will follow-up with the investigator regarding additional information that may be requested.

If a female subject becomes pregnant during the study, the investigator should attempt to obtain information regarding the birth outcome and health of the infant.

If the outcome of the pregnancy meets a criterion for immediate classification as a Serious Adverse Event (eg, female subject experiences a spontaneous abortion, stillbirth, or neonatal death or there is a fetal or neonatal congenital anomaly) the investigator will report the event as a Serious Adverse Event.

If a female breastfeeds following exposure to the Amgen Investigational Product (AMG 890 or placebo) report the lactation case to Amgen as specified below.

In addition to reporting a lactation case during the study, investigators should report lactation cases that occur through 90 days after receiving the Amgen Investigational Product (AMG 890 or placebo) for subjects who withdraw prior to end of study.

Any lactation case should be reported to Amgen Global Patient Safety within 24 hours of the Investigator's knowledge of event. Report a lactation case on the Lactation Notification Worksheet ([Appendix C](#)). Amgen Global Patient Safety will follow-up with the investigator regarding additional information that may be requested.

If a male subject's female partner becomes pregnant, the investigator should discuss obtaining information regarding the birth outcome and health of the infant from the pregnant partner.

### **13. STATISTICAL CONSIDERATIONS**

#### **13.1 Study Endpoints, Analysis Sets, and Covariates**

##### **13.1.1 Study Endpoints**

###### **13.1.1.1 Primary Endpoints**

- Subject incidence of treatment-emergent adverse events
- Safety laboratory analytes, vital signs, and electrocardiograms (ECGs)

###### **13.1.1.2 Secondary Endpoints**

- AMG 890 PK parameters including, but not limited to, maximum observed concentration ( $C_{max}$ ), the time of maximum observed concentration ( $t_{max}$ ), and area under the concentration-time curve (AUC)
- Pharmacodynamic parameters:
  - Change and percent change in plasma Lp(a) levels at each scheduled visit up to the end of treatment visit

###### **13.1.1.3 Exploratory Endpoints**

- Change and percent change in total cholesterol and cholesterol fractions (very-low density lipoprotein cholesterol [VLDL-C], low-density lipoprotein cholesterol [LDL-C], and high-density lipoprotein cholesterol [HDL-C]), triglycerides, apolipoprotein A1 (ApoA1) and total apolipoprotein B (ApoB) at each scheduled visit
- AMG 890 excretion in urine

##### **13.1.2 Analysis Sets**

For all analyses, subjects will be analyzed according to the dose and treatment they received, not the dose and treatment to which they were randomized.

###### **13.1.2.1 Safety Analysis Set**

The safety analysis set will consist of all study subjects who receive at least 1 dose of AMG 890 or placebo.

Subjects withdrawing prior to AMG 890 or placebo administration due to adverse events related to study procedure will not be included in the safety analysis set but those adverse events will be listed.

#### **13.1.2.2 Pharmacokinetic (PK) Analysis Set**

The PK analysis set will consist of all dosed subjects for whom at least 1 PK parameter or endpoint can be reliably estimated.

#### **13.1.2.3 Pharmacodynamics (PD) Analysis Set**

The PD analysis set will consist of all dosed subjects for whom at least 1 PD parameter has a baseline value and at least 1 post-baseline measurement available. Baseline values for Lp(a) are defined as the mean of screening and day 1 predose. If for any reason only 1 value is available, then that value will be used as baseline.

#### **13.1.2.4 Covariates and Subgroups**

Baseline values may be used as a covariate in analyses. For any variable, unless otherwise defined, baseline is defined as the last assessment taken prior to the first administration of AMG 890 or placebo.

No subgroup analyses are planned.

#### **13.1.3 Handling of Missing and Incomplete Data**

The frequency of missing and incomplete data is expected to be low in this study and therefore, missing data will not be imputed.

### **13.2 Sample Size Considerations**

The sample size is based on practical considerations. Approximately █ subjects will be enrolled. With at least 6 subjects receiving AMG 890 in each cohort, there is at least a 74% chance of detecting an adverse event (AE) with a true incidence of 20% within each cohort. With at least 10 subjects receiving both AMG 890 and statin, there is at least an 89% chance of detecting an adverse event with a true AE incidence rate of 20%. With █ subjects receiving AMG 890 there is a 95% chance of detecting an adverse event with a true incidence of 5%.

#### **13.3 Access to Individual Subject Treatment Assignments by Amgen or Designees**

Blinded individuals will not have access to unblinded information until the study is formally unblinded. Amgen staff and their designees involved in the study will not be blinded, but will only be given treatment assignments when there is a need to use the information for analysis, discussion and internal decision making. The Amgen Medical

Monitor will be unblinded to treatment assignment throughout the duration of the study. Access to treatment assignments and other restricted data are described in Amgen standard documents. Unblinded individuals are to ensure unblinding and potentially unblinding information should not be distributed to the investigators or subjects prior to the study being formally unblinded.

#### **13.4       Planned Analyses**

##### **13.4.1      Data Monitoring Committee (DMC), Data Review Team (DRT) or Dose Level Review Team (DLRT)**

The DLRT voting members are responsible for dose level recommendations. The key objectives of the DLRT are to review data, monitor safety, and make dose change recommendations. Except for the unblinded Amgen Medical Monitor who will review data in an unblinded manner, DLRMs will be conducted in a blinded manner. Please refer to Section [9.2.4.1](#) for details.

##### **13.4.2      Primary Analysis**

The primary analysis will occur after all subjects have completed the end of treatment visit.

##### **13.4.3      Final Analysis**

The final analysis will occur after all subjects have completed the study.

#### **13.5       Planned Methods of Analysis**

##### **13.5.1      General Considerations**

Descriptive statistics will be provided for selected demographics, adverse events, vital signs, ECG, PK, and selected laboratory measurements. Descriptive statistics on continuous measurements will include means, medians, standard deviations, and ranges, while categorical data will be summarized using frequency counts and percentages. Data will be presented and summarized by treatment cohort and at each time point. Graphical summaries of the data may also be presented.

Data for subjects receiving placebo will be combined across cohorts 1 to 5 and separately across cohorts 6 to 9.

When data are summarized by time, the values recorded against the scheduled time points listed in the protocol will be used. When assessing minimum/maximum increases or decreases over the study, all assessments, including unscheduled assessments will be used. Unless stated otherwise in the statistical analysis plan, the data analysis will be conducted using subjects in the safety analysis set. For statistical analyses

comparing change from baseline, only subjects with both baseline and at least 1 post-baseline assessment will be included.

At the primary analysis, the primary, secondary, and exploratory endpoints (if applicable) will be analysed. All data up to each subject's end of treatment visit will be included in the primary analysis. The follow-up time points will be summarized at the final analysis.

**13.5.2 Primary Endpoint(s)**

**13.5.2.1 Safety Endpoint(s)**

**13.5.2.1.1 Adverse Events**

All subjects who receive a dose of AMG 890 or placebo in the safety analysis set will be included in the analysis of the primary endpoints. Subject incidence of all treatment-emergent adverse events will be tabulated by system organ class and preferred term according to the medical dictionary for regulatory activities (MedDRA) terminology. Tables of fatal adverse events, serious adverse events, adverse events leading to withdrawal from IP or other protocol-required therapies, and significant treatment emergent adverse events will also be provided if observed. The number and percentage of subjects reporting adverse events will be evaluated for each dose cohort and across dose cohorts.

**13.5.2.1.2 Vital Signs**

Vital signs will be listed and reviewed for each subject. Summaries of heart rate and blood pressure data over time and change from baseline will be provided. The analyses of vital signs will include summary statistics over time (for each protocol scheduled study visit) by cohort. Depending on the size and scope of changes, summaries of changes from baseline over time may be provided.

**13.5.2.1.3 Electrocardiogram**

For cohorts 1 to 5 and cohorts 8 and 9, summaries over time and/or changes from baseline over time will be provided for ECG parameters (eg, RR, PR, QRS, QTc). Subjects' maximum change from baseline in QTc will be categorized and the number and percentage of subjects in each group will be summarized. Subjects' maximum post-baseline values will also be categorized and the number and percentage of subjects in each group will be summarized. Baseline ECG recording is defined as the mean of the 3 sets of triplicate ECG results (a total of 9 assessments) at study day -1 for cohorts 1 to 5, and at the day -3 to -1 visit for cohorts 8 and 9.

For cohorts 6 and 7, the ECG measurements will be performed as per standard of care for routine safety monitoring, rather than for purposes of assessment of potential QTc effect. Since these evaluations may not necessarily be performed under the rigorous conditions expected to lead to meaningful evaluation of QTc data; summaries and statistical analyses of ECG measurements are not planned, and these data would not be expected to be useful for meta-analysis with data from other trials.

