**Table 1. Planned Treatment by Cohort**

| Cohort           | Number of Subjects | Investigational Product (SC administration) |
|------------------|--------------------|---|
| 1 a   | 6                  | AMG 890 3 mg                                |
|                  | 2                  | Placebo                                     |
| 2 a   | 6                  | AMG 890 9 mg                                |
|                  | 2                  | Placebo                                     |
| 3 a   | 6                  | AMG 890 30 mg                               |
|                  | 2                  | Placebo                                     |
| 4 a   | 6                  | AMG 890 75 mg                               |
|                  | 2                  | Placebo                                     |
| 5 a   | 6                  | AMG 890 225 mg                              |
|                  | 2                  | Placebo                                     |
| 6 b,s | 9                  | AMG 890 9 mg                                |
|                  | 3                  | Placebo                                     |
| 7 b,s | 9                  | AMG 890 75 mg                               |
|                  | 3                  | Placebo                                     |
| 8 b,s | 6                  | AMG 890 225 mg                              |
|                  | 2                  | Placebo                                     |
| 9 b,s | 6                  | AMG 890 675 mg                              |
|                  | 2                  | Placebo                                     |

a = subjects with screening plasma Lp(a)  $\geq$  70 nmol/L and  $\leq$  199 nmol/L

b = subjects with screening plasma Lp(a)  $\geq$  200 nmol/L

s = at least 6 subjects must be on a stable dose of a statin for at least 6 weeks in each of cohorts 6 to 9

As described in the Eligibility Criteria, cohorts 1 to 5 will enroll subjects with plasma Lp(a) between 70 nmol/L and 199 nmol/L, inclusive. Cohorts 6 to 9 will enroll subjects with plasma Lp(a) equal to or greater than 200 nmol/L. At least 6 subjects in each of cohorts 6 to 9 will be on a stable dose of statin for at least 6 weeks.

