## 6. EXPERIMENTAL PLAN

### 6.1 Study Design

This is a FIH randomized, double-blind, placebo-controlled, single ascending dose (SAD) study in subjects with elevated plasma Lp(a). AMG 890 will be evaluated as SC injections in adult subjects. Approximately █ subjects will enroll in 9 SAD cohorts. As described in [Table 1](#), for each cohort, subjects will be randomized to receive AMG 890 or placebo SC in a 3:1 ratio. As of Amendment 6, enrollment in cohorts 1 to 8

is closed. There were no safety concerns noted that would preclude enrollment into the higher dose cohorts, 8 and 9.

As described in the Eligibility Criteria (Section 7), cohorts 1 to 5 will enroll subjects with plasma Lp(a) between 70 nmol/L and 199 nmol/L, inclusive. Cohorts 6 to 9 will enroll subjects with plasma Lp(a) equal to or greater than 200 nmol/L. In cohorts 6 to 9, at least 6 subjects in each cohort will be on a stable dose of statin.

For cohorts 1 to 5, and cohort 9, the first 2 enrolled subjects will be randomized in a 1:1 ratio (sentinel pair) and will be dosed on the same day at the same study site. Within the pair and while maintaining treatment blind, 1 subject will receive AMG 890 and the other subject will receive placebo. If deemed safe by the investigator after review of available safety data at least 24 hours after the sentinel pair is dosed, the same dose will be administered to the remaining subjects of the cohort.

Enrollment into cohorts 1 to 5 will be staggered. Escalation to the next cohort will occur after the assessment of the safety and tolerability of each dose level. The recommendation to dose escalate will be based on the blinded review of safety data (including but not limited to vital signs, ECGs, treatment emergent adverse events, and clinical laboratory results) during the DLRM. Within each cohort, the safety data will be assessed after all 8 subjects have been enrolled and have been followed for 15 days. Emerging PD data may be reviewed in a blinded fashion at the DLRM as the data become available. The Dose Level Review Team (DLRT) will be responsible for dosing recommendations, which may include escalation to the next planned dose, adding additional cohorts, escalation to an intermediate dose (a dose lower than the next planned dose), de-escalation to a lower dose; continuation, delay, or termination of dosing; or repetition or expansion of a cohort.

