## Electrocardiograms

The subject must be in a supine position in a rested and calm state for at least 5 minutes before ECG assessment is conducted. If the subject is unable to be in the supine position, the subject should be in most recumbent position as possible.

The Screening ECG will be performed as a single ECG for screening purposes.

For cohorts 1 to 5, day -1 pre-dose ECGs will be performed on 3 occasions separated by at least 30 minutes all in triplicate for a total of 9 ECGs (3 sets of triplicate). This is the baseline ECG. At all other time points, ECGs will be performed in a standardized method, in triplicate, and approximately 30 seconds apart, prior to blood draws or other invasive procedures. Each ECG must include the following measurements: QRS, QT, QTc, RR, and PR intervals.

For cohorts 6 and 7, all ECGs will be performed as a single ECG for all time points, and prior to blood draws or other invasive procedures. The ECG must include the following measurements: Heart Rate, QRS, QT, QTc, and PR intervals.

For cohorts 8 and 9, the screening ECG will be performed as a single trace. The day -3 to -1 pre-check visit ECG will be the Baseline ECG and will be performed on 3 occasions separated by at least 30 minutes, all in triplicate for a total of 9 ECGs (3 sets of triplicates). Each set of triplicate ECGs should be run consecutively and completed within a total of 5 minutes from the start of the first to the completion of the third. For ECGs at 2, 3, 6, 9, 24, and 72 hours post-dose, ECGs will be performed in a

standardized method, in triplicate and run consecutively (triplicate ECGs should be completed within a total of 5 minutes from the start of the first to the completion of the third). ECGs will be performed prior to blood draws or other invasive procedures. At all other time points after 72 hours post-dose, ECGs will be performed as a single trace and prior to blood draws or other invasive procedures. Each ECG must include the following measurements: QRS, QT, QTc, RR, and PR intervals.

The investigator or designated site physician will review all ECGs. Once signed, the original ECG tracing will be retained with the subject's source documents. At the request of the sponsor, a copy of the original ECG will be made available to Amgen or designee.

Standard ECG machines provided by the sponsor should be used for all study-related ECG procedures.

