4.2 Subgroups

No subgroup analysis is planned.

5. Definitions

Age at time of enrollment

Subject age in years at time of enrollment will be collected in the clinical database.

AUC_{last}

Area under the concentration-time curve from time zero to the last quantifiable concentration.

AUC_{inf}

Area under concentration-time curve from time 0 extrapolated to infinity.

Baseline

Baseline values for Lp(a) are defined as the mean of screening and day 1 predose. If for any reason only 1 value is available, then that value will be used as baseline.

For any other variable, unless otherwise specified, baseline is defined as the last assessment taken prior to administration of AMG 890 or placebo.

ECG Baseline value

Analysis of ECG is applicable to cohorts 1 to 5 and 8 and 9 only.

Baseline ECG for cohorts 1 to 5 is defined as the mean of the triplicate values measured on Day -1. Baseline ECG for cohorts 8 and 9 is defined as the mean of the 3 triplicate values measured at the Day -3 to -1 dosing pre check visit. If there are any missing values, the mean of the non-missing values will be taken as baseline.

Change from Baseline

Change from baseline is the arithmetic difference between post-baseline and baseline.

Enrollment Date

Enrollment date is defined as the date on which subject was enrolled in the study.

End of Study for the Overall Trial

Defined as when the last subject is assessed or receives an intervention for evaluation in the study i.e. last subject last visit, following any additional parts in the study (e.g. Follow-up period, long term follow-up) as applicable.

End of Study for Individual Subject

Defined as the last date recorded on the End of Study form for an individual subject.

End of Treatment Date

End of Treatment Date for cohort 1 and 2 is the date of Day 113 visit, for Cohort 3 to 7 is the date of Day 225 visit and for cohort 8 and 9 is the date of Day 365 visit.

Fridericia-corrected QT Interval (QTcF)

The Fridericia correction will be calculated from the investigator reported QT (msec) and RR interval (msec), as follows:

$$\text{QTcF} = \text{QT}/\text{RR}^{1/3}$$

Investigational Product

The term investigational product is used in reference to AMG 890 or placebo.

Percentage Change from Baseline

Percentage change from baseline is arithmetic difference between post baseline and baseline divided by baseline values times 100.

Randomization Date

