9.6.5 Electrocardiogram

Each ECG will include following measurements: PR, QRS, QT, QTc, RR.

The following summary will be provided for cohorts 1 to 5 and Cohorts 8 and 9 only.

Summaries over time and change and percentage change from baseline over each scheduled time points (including time points with single and triplicate measurements) will be provided for each ECG parameter by treatment group and cohort.

Further subjects' maximum change from baseline in QTcF will be categorized in following categories and the number and percentage of subjects in each treatment group and cohort will be summarized. Unscheduled assessments will be included in the determination of the maximum change.

<=30 msec

>30-60 msec

>60 msec

Subjects' maximum post baseline values in QTcF will also be categorized in the following categories and the number and percentage of subjects in each treatment group and cohort will be summarized. Unscheduled assessments will be included in the determination of the maximum post baseline value.

<=450 msec

>450-480 msec

>480-500 msec

>500 msec

Subject level data listing will be reviewed.

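### ECG is a primary endpoint, but cohorts 6 and 7 have no ECG summary of any kind; the stated reason justifies omitting QTc means and small changes, not a count of marked outliers

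*Protocol*

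**What the plan says.** Protocol 13.1.1.1 lists among the primary endpoints "Safety laboratory analytes, vital signs, and electrocardiograms (ECGs"), with no limit by cohort. Protocol 13.5.2.1.1, under Adverse Events, puts every dosed subject in the safety analysis set into the analysis of the primary endpoints. For the statin objective, SAP 2.1 undertakes to report both primary and secondary endpoints in subjects taking statins.

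Protocol 13.5.2.1.3 plans ECG summaries and QTc categories for cohorts 1 to 5, 8 and 9. For cohorts 6 and 7 "summaries and statistical analyses of ECG measurements are not planned", because the recordings are routine safety monitoring and may not meet the conditions needed to evaluate QTc. The ECG baseline entry in SAP Section 5 agrees: "Analysis of ECG is applicable to cohorts 1 to 5 and 8 and 9 only". SAP 9.6.5 repeats the limit. For the cohorts in scope, it summarises every scheduled time point, "including time points with single and triplicate measurements".

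Protocol 10.3 (Electrocardiograms) has all ECGs in cohorts 6 and 7 taken as single traces. In cohorts 8 and 9, every ECG after 72 hours is also a single trace. The supine rest rule and the timing before blood draws are the same for both groups, and "Standard ECG machines provided by the sponsor should be used for all study-related ECG procedures".

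**The concern.** A primary endpoint is collected in cohorts 6 and 7 and then reported nowhere in aggregate. The reason given concerns QTc alone, yet PR and QRS are dropped as well. Single traces recorded under the same rest, timing and equipment rules are used in cohorts 8 and 9.

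These two cohorts are the only ones that give 9 mg and 75 mg to subjects with Lp(a) at or above 200 nmol/L. They also hold half of the required minimum of statin users. As planned, a reader of the study report could not tell from any ECG table whether a subject in these cohorts had a QTcF above 500 msec. The two commitments above would also go unmet for ECG, and SAP Section 10 does not mention this.

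**Working it through.** **1. Subjects affected.** The text totals are redacted, so the counts come from Table 1.
- AMG 890: 5×6 + 9 + 9 + 6 + 6 = 60. Cohorts 6 and 7: 9 + 9 = 18, and 18/60 = 30%.
- Placebo: 5×2 + 3 + 3 + 2 + 2 = 20. Cohorts 6 and 7: 3 + 3 = 6, and 6/20 = 30%.
- Active subjects with Lp(a) ≥ 200 nmol/L: 18 of 9 + 9 + 6 + 6 = 30, or 60%.
- Minimum statin users, active plus placebo: 2×6 = 12 in cohorts 6 and 7, out of 4×6 = 24 in cohorts 6 to 9.

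The total of 60 agrees with Protocol 13.2. The chance of at least one event is 1 − (1 − p)^n. With n = 60 and p = 0.05 it is 1 − 0.95^60 = 95.4%, against the stated 95%. The other two stated figures also reproduce: 1 − 0.8^6 = 73.8% (stated 74%) and 1 − 0.8^10 = 89.3% (stated 89%). All three refer to adverse events and are used here only to check the count.

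**2. Does the stated reason reach each ECG output?**

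| Feature | Cohorts 6 and 7 | Cohorts 8 and 9 |
|---|---|---|
| Baseline | one trace, day -3 to -1 | mean of nine ECGs |
| First 72 hours | one ECG, on day 1 | triplicates at 2, 3, 6, 9, 24 and 72 h |
| After 72 hours | single traces | single traces |
| Rate variable required | heart rate | RR |
| Rest, timing before blood draws, machines | same rules | same rules |

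- Mean change and the >30-60 msec category depend on a precise baseline and dense early sampling. The reason holds for these.
- Maximum post-baseline QTcF above 480 or 500 msec needs no baseline. SAP 9.6.5 does not confine this category to triplicates, so later single traces in cohorts 8 and 9 count. The reason does not hold here.
- Change above 60 msec uses a baseline, so the question is whether single-trace noise would create false cases.

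**3. Noise check.** Assumptions, none of them from the documents: independent normal within-subject errors, SD σ of 8 to 12 msec, and no true change. Tables 6 and 7 show six post-dose ECGs (day 1, then days 7, 29, 57, 155 and end of treatment). The chance that the largest of six exceeds a single baseline by more than c is

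P = ∫ φ(b) [1 − Φ(b + c/σ)^6] db.

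| σ (msec) | P(change > 30) | P(change > 60) |
|---|---|---|
| 8 | 2.0% | < 0.001% |
| 10 | 7.4% | 0.006% |
| 12 | 15.0% | 0.11% |

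Across 24 subjects at σ = 12, chance alone gives 24 × 0.0011 = 0.03 expected cases above 60 msec, but 24 × 0.150 = 3.6 above 30 msec. The higher cut-off is usable with single traces and the lower one is not.

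**The case against.** The restriction is deliberate, prespecified, explained and consistent between protocol and SAP. It rests on real differences in baseline, early sampling and rate variable. Monkey half-life was 3.13 to 5.09 hours (Protocol 5.2.2), so if humans are similar most traces in cohorts 6 and 7 fall after serum clearance. Predicted Cmax at 9 and 75 mg is 30.1 and 251 ng/mL, against 753 and 2260 ng/mL at 225 and 675 mg. Those higher exposures are studied with early triplicates in the same Lp(a) stratum. The sentence about all dosed subjects sits under Adverse Events and may not have been written with ECG in mind. All of this stands. It rules out a full QTc analysis of cohorts 6 and 7 and keeps the point modest. It does not answer the SAP 2.1 commitment on statin users or explain why no count of marked outliers is reported.

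Three stronger readings are tempting, and the documents do not support them:
- *ECG harm in cohorts 6 and 7 would go unseen.* Investigators read every ECG, the unblinded medical monitor reviews data throughout, ECGs go to dose level review, and an ECG-related adverse event enters the adverse event tables. SAP 9.6.5 also has a subject-level listing reviewed, without saying whether it includes these cohorts.
- *The omission breaks the stated 89% or 95% detection chances.* Those figures are for adverse events, and cohorts 6 and 7 stay in every treatment-period adverse event table.
- *The exclusion thins the placebo comparator for cohorts 8 and 9, and the remedy would restore it.* A separate outlier table leaves that comparator as it is, and pooling single-trace-baseline placebo subjects into the QTc means would run against the valid part of the sponsor's reason.

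**Conclusion.** The point holds as a gap in the reported ECG tables. For 18 of 60 planned AMG 890 subjects and 6 of 20 placebo subjects, a primary endpoint has no planned summary, contrary to the plain wording of Protocol 13.5.2.1.1 and SAP 2.1. The protocol's reason justifies leaving out mean QTc changes and small-change categories. It does not justify leaving out marked outliers. Safety oversight is not in question, and no stated detection probability is missed. This is a cheap improvement to reporting.

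The counts assume Table 1 as planned; the option to expand cohorts 1 to 5 would lower the 30% share. The statement that chance changes above 60 msec are rare assumes a within-subject SD of 8 to 12 msec and normal errors. It does not cover recording artefacts.

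**What to change.** In SAP 9.6.5, keep mean changes and the >30-60 msec category for cohorts 1 to 5, 8 and 9 only. Add one table for cohorts 6 and 7, by AMG 890 cohort and with their 6 placebo subjects pooled. It should give the number and percentage with any post-dose QTcF above 480 msec, above 500 msec, or more than 60 msec above the last pre-dose trace. The last pre-dose value is already the SAP Section 5 default baseline. Derive RR as 60 / heart rate, in seconds, so that QT / RR^(1/3) comes out on the msec scale of the cut-offs. Footnote the table as single-trace data.

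State that the subject-level ECG listing covers cohorts 6 and 7. Amend the ECG entry in SAP Section 5, reconcile Protocol 13.5.2.1.1 and SAP 2.1 with Protocol 13.5.2.1.3, and declare the change in SAP Section 10.

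The cost is one small table from data already collected. The downside is that an occasional artefact may have to be checked against the tracing. PR and QRS would still appear only in the listing.
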